8.6 Vital Signs

Vital signs will include blood pressure (diastolic and systolic), heart rate, and body temperature, and will be collected at Screening, Days 1, 3, 5, and EOT, as well as at the PTE. During the Follow-up call/visit vital signs are collected if the subject reports symptoms of potential recurrence and clinic visit is required.

Additionally, height will be collected at the Screening visit, and body weight will be collected at the Screening and EOT visits.

Blood pressure (systolic and diastolic) and heart rate will be summarized by time point and for the minimum and maximum post-baseline values using descriptive statistics, for both the actual values and the change from baseline.

Figures (line graphs) of observed values for heart rate, systolic and diastolic blood pressure over time will also be provided by treatment group.

Post-baseline vital signs will be defined as CN if they meet 1) the criterion value at the given visit, or 2) meet both the criterion value and the change from baseline criterion listed in [Table 11](#). The incidence of CN vital signs will be summarized by time point and treatment group and will be listed and flagged in by-subject listings. An overall post-baseline incidence of CN values for each vital sign parameter, will also be summarized. A separate listing will be provided of subjects with values for a vital sign noted as CN.

Table 11 Criteria for Clinically Notable Vital Signs

Vital Sign Parameter	Flag	Criterion Value	Change from Baseline
Systolic Blood Pressure (mmHg)	High (CH)	≥ 180	Increase of ≥ 20 mmHg
	Low (CL)	≤ 90	Decrease of ≥ 20 mmHg
Diastolic Blood Pressure	High (CH)	≥ 105	Increase of ≥ 15 mmHg

Table 11 Criteria for Clinically Notable Vital Signs

Vital Sign Parameter	Flag	Criterion Value	Change from Baseline
(mmHg)	Low (CL)	≤ 50	Decrease of ≥ 15 mmHg
	High (CH)	≥ 120	Increase of ≥ 15 bpm
Heart Rate (bpm)	High (CH)	≥ 120	Increase of ≥ 15 bpm
	Low (CL)	≤ 50	Decrease of ≥ 15 bpm

8.7 Pregnancies

Results of local (urine or serum) and central (serum) pregnancy tests will be listed for all subjects enrolled in the study by treatment group. It is expected for pregnancy counts to be small and thus narratives will be provided in the CSR.

9 CHANGES FROM PROTOCOL

Not applicable.

APPENDIX 1 CLINICAL LABORATORY TESTS (CENTRAL)**Table 12 Clinical Laboratory Tests (Central)**

Hematology:	Serum Chemistry:

 • Hematocrit (Hct) • Hemoglobin (Hgb) • Mean corpuscular hemoglobin (MCH) • Mean corpuscular hemoglobin concentration (MCHC) • Mean corpuscular volume (MCV) • Platelet count • Red blood cell (RBC) count • White blood cell (WBC) count with differential 	
 • Albumin (ALB) • Alkaline phosphatase (ALP) • Alanine aminotransferase (ALT) • Amylase • Aspartate aminotransferase (AST) • Blood urea nitrogen (BUN) • Calcium (Ca) • Carbon dioxide (CO₂) • Chloride (Cl) • Creatinine • Creatine phosphokinase (CK) • Gamma-glutamyl transpeptidase (GGT) • Glucose • Lactate dehydrogenase (LDH) • Lipase • Magnesium • Phosphorus (P) • Potassium (K) • Sodium (Na) • Total bilirubin • Total protein • Uric acid

Coagulation:
 
 • Ratio of prothrombin time (PT) and international normalized ratio (INR) 	

Pregnancy (all subjects):
 
 • Serum β-human chorionic gonadotropin (β-HCG) 	

Urinalysis:
 
 • Bilirubin • Glucose • Ketones • Leukocyte esterase • Microscopic examination of sediment with WBC count • Nitrites • Occult blood • potential of hydrogen (pH) • Protein • Specific gravity • Urobilinogen 	

APPENDIX 2 DIRECTIONALITY OF WORST LABORATORY PARAMETERS

Laboratory Test	Parameter	Worst Value
Hematology	Hematocrit	Lowest value
	Hemoglobin	Lowest value
	Red blood cell count	Lowest value
	Mean cell hemoglobin	Lowest value
	Mean cell hemoglobin concentration	Lowest value
	Mean cell volume	Lowest value
	White blood cell count	Lowest value
	Platelets	Lowest value
	Neutrophils	Lowest value
	Lymphocytes	Lowest value
	Monocytes	Lowest value
	Eosinophils	Highest value
	Basophils	Lowest value
	Chemistry	Albumin
Alkaline phosphatase		Highest value
Alanine aminotransferase (ALT/SGPT)		Highest value
Amylase		Highest value
Aspartate aminotransferase (AST/SGOT)		Highest value
Urea		Highest value
Bicarbonate		Lowest value
Calcium		Both highest value and lowest value
Cholesterol		Highest value
Chloride		Both highest value and lowest value
Creatinine		Highest value
Creatine kinase (CK)		Highest value
Gamma-glutamyl transpeptidase (GGT)		Highest value
Blood glucose		Both highest value and lowest value
Lactate dehydrogenase (LDH)		Highest value
Lipase		Highest value
Magnesium		Both highest value and lowest value
Phosphate		Both highest value and lowest value
Potassium		Both highest value and lowest value
Sodium		Both highest value and lowest value
Total bilirubin		Highest value
Total protein	Lowest value	
Uric acid	Highest value	
Coagulation	International normalized ratio (INR)	Highest value

APPENDIX 3 MODIFIED DIVISION OF MICROBIOLOGY AND INFECTIOUS DISEASES ADULT TOXICITY TABLE

The DMID Adult Toxicity Table (21-Nov-2007) was modified to exclude the clinical component of the toxicity grading because clinical signs and symptoms related to abnormal laboratory values are not collected in this study. In addition, Grade 0 was added to the table so that shifts from normal could be analyzed. The grades for several parameters including enzymes were modified to ensure that any possible numeric value can be categorized appropriately (eg, for creatinine, Grade 3 is defined as “>1.5-3.0×ULN” instead of “1.6-3.0×ULN”).

For toxicity grades based on a multiple of the ULN, the normal range from the central laboratory will be applied.

For toxicity grades based on fixed values, the grades will be assigned regardless of the normal actual range values from the central laboratory. For example, a hemoglobin value of 10.0 gm/dL will be assigned a grade 1 toxicity, even if the lower limit of normal from the laboratory was 9.8 gm/dL.

HEMATOLOGY

	Grade 0	Grade 1	Grade 2	Grade 3	Grade 4
Hemoglobin (gm/dL)	> 10.5	9.5-10.5	8.0-9.4	6.5-7.9	< 6.5
Absolute Neutrophil Count (count/mm ³)	> 1500	1000-1500	750-999	500-749	< 500
Platelets (count/mm ³)	≥ 100,000	75,000-99,999	50,000-74,999	20,000-49,999	< 20,000
WBCs (count/mm ³)	1000-10,999	11,000-12,999	13,000-14,999	15,000-30,000	> 30,000 or < 1,000

COAGULATION

	Grade 0	Grade 1	Grade 2	Grade 3	Grade 4
Prothrombin time (PT) (sec)	≤1 x ULN	1.01-1.25 x ULN	1.26-1.5 x ULN	1.51 - 3.0 x ULN	> 3 x ULN
International normalized ratio (INR)	Increased	≤ ULN	> 1 - 1.5 x ULN	> 1.5 - 2.5 x ULN	> 2.5 x ULN

CHEMISTRY

	Grade 0	Grade 1	Grade 2	Grade 3	Grade 4
Hyponatremia (mEq/L) (Na)	> 135	130-135	123-129	116-122	< 116
Hypernatremia (mEq/L) (Na)	< 146	146-150	151-157	158-165	> 165
Hypokalemia (mEq/L) (K)	> 3.4	3.0-3.4	2.5-2.9	2.0-2.4	< 2.0
Hyperkalemia (mEq/L) (K)	< 5.6	5.6-6.0	6.1-6.5	6.6-7.0	> 7.0
Hypoglycemia (mg/dL) (glucose)	≥ 65	55-64	40-54	30-39	< 30
Hyperglycemia (mg/dL) (nonfasting and regardless of prior history of diabetes) ¹ (glucose)	< 116	116-160	161-250	251-500	> 500
Hypocalcemia (mg/dL) (corrected for albumin) ² (Ca)	> 8.4	8.4-7.8	7.7-7.0	6.9-6.1	< 6.1
Hypercalcemia (mg/dL) (correct for albumin) ² (Ca)	≤ 10.5	10.6-11.5	11.6-12.5	12.6-13.5	> 13.5
Hypomagnesemia (mEq/L) (Magnesium)	> 1.4	1.4- 1.2	1.1-0.9	0.8-0.6	< 0.6
Hypophosphatemia (mg/dL) (P)	≥ 2.5	2.0-2.4	1.5-1.9	1.0-1.4	< 1.0
Hyperbilirubinemia (total bilirubin)	< 1.1×ULN	1.1-1.5×ULN	> 1.5-2.5×ULN	> 2.5-5×ULN	> 5×ULN
Urea	< 1.25×ULN	1.25-2.5×ULN	> 2.5-5×ULN	> 5-10×ULN	>10×ULN
Hyperuricemia (uric acid) (mg/dL)	< 7.5	7.5–10.0	10.1–12.0	12.1–15.0	> 15.0
Creatinine	< 1.1×ULN	1.1-1.5×ULN	> 1.5-3.0×ULN	> 3.0-6×ULN	> 6×ULN

¹ The DMID toxicity table reports hyperglycemia detected in nonfasting specimens obtained from subjects with no prior diabetes.

² Calcium corrected for albumin = [0.8 x (normal albumin - subject's albumin)] + serum Ca level
Where normal albumin = 4 g/dl, albumin is in g/dL and calcium is in mg/dL

ENZYMES

	Grade 0	Grade 1	Grade 2	Grade 3	Grade 4
AST (SGOT)	< 1.25×ULN	1.25-2.5×ULN	> 2.5-5×ULN	> 5-10×ULN	> 10×ULN
ALT (SGPT)	< 1.25×ULN	1.25-2.5×ULN	> 2.5-5×ULN	> 5-10×ULN	> 10×ULN
GGT	< 1.25×ULN	1.25-2.5×ULN	> 2.5-5×ULN	> 5-10×ULN	> 10×ULN
Alkaline Phosphatase	< 1.25×ULN	1.25-2.5×ULN	> 2.5-5×ULN	> 5-10×ULN	> 10×ULN
Amylase	< 1.1×ULN	1.1-1.5×ULN	> 1.5-2.0×ULN	> 2.0-5.0×ULN	> 5.0×ULN
Lipase	< 1.1×ULN	1.1-1.5×ULN	> 1.5-2.0×ULN	> 2.0-5.0×ULN	> 5.0×ULN

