9.5 Follow-up Phase

9.5.1 Post-Treatment Evaluation (PTE) Visit

The PTE visit should be conducted on Day 14 (+/- 2 days) after the subject’s first dose of test article. This evaluation should also be conducted for any prematurely withdrawn subject. The following assessments will be performed at the PTE visit:

- Subject assessment of UTI signs and symptoms severity (UTISA questionnaire)
- Physical examination
- Concomitant medications
- Laboratory tests (urine):
 - Urinalysis via dipstick with optional microscopic exam
 - Urine culture
- Vital signs: body temperature, blood pressure, heart rate
- Laboratory tests (blood):
 - hematology (includes coagulation) *
 - chemistry *
 - serum pregnancy test

*Note: hematology & chemistry will be performed only if clinically significant abnormalities were noted at EOT
- AEs
- Investigator’s assessment of clinical response

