8.5 Clinical Laboratory Results

Clinical laboratory safety assessments include hematology (including coagulation), serum chemistry, and urinalysis.

Clinical laboratory parameters include those listed in the [Appendix 1 Clinical Laboratory Tests \(Central\)](#).

Baseline is defined as the central lab value closest to and prior to the first dose of test article. If no central lab value is available prior to the first dose of study drug, the local lab value that is closest to and prior to the first dose of study drug will be used as baseline. For by visit analyses, central lab values will be used unless no central lab value was obtained in the visit window. In this case, local lab values will be used for the by visit analyses. All lab values (central and local) are used for determination of the overall worst post-baseline value.

Laboratory data will be summarized by timepoint and for the overall worst post-baseline value using descriptive statistics (based on International System [SI] units) for the actual results and change from baseline for hematology and serum chemistry assessments.

Descriptive statistics (based on SI units) for chemistry, hematology and coagulation values and the change from baseline will be summarized by treatment group at each time point, and for the overall worst value post-baseline (which includes unscheduled visits).

[Appendix 2 Directionality of Worst Laboratory Parameters](#) provides the directionality of the worst values for each laboratory parameter.

Clinically notable laboratory values will be determined based on the modified Division of Microbiology and Infectious Diseases (DMID) criteria in [Appendix 3 Modified Division of Microbiology and Infectious Diseases Adult Toxicity Table](#).

Shift tables will be presented to show the number of subjects with a laboratory value with a grade of 0, 1, 2, 3 or 4 at baseline versus the value at each visit. Number and percentage of subjects with at least a 2-grade increase from baseline (based on DMID criteria) will be summarized by treatment arm. Percentages for each laboratory test will be based on the number of subjects with a baseline and post-baseline evaluation of the specific laboratory test. A listing will be provided for subjects who have at least a 2-grade increase from baseline in a given laboratory test.

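### SAP Appendices 2 and 3 treat white cell counts inconsistently: falls to as low as 1,000/mm3 get no grade shift, and the worst-value summary omits high counts

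*SAP*

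**What the plan says.** **Grading.** SAP Appendix 3 adapts an external toxicity table and states that "Grade 0 was added to the table so that shifts from normal could be analyzed", so Grade 0 is the SAP's own addition and stands for normal. In the WBC row (count/mm3), Grade 0 is 1,000 to 10,999, Grade 1 is 11,000 to 12,999, Grade 2 is 13,000 to 14,999, Grade 3 is 15,000 to 30,000, and Grade 4 is "> 30,000 or < 1,000". For rows with fixed limits, such as this one, "the grades will be assigned regardless of the normal actual range values from the central laboratory".

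**Direction of worst.** The Appendix 2 entry reads "White blood cell count Lowest value". For sodium, potassium, calcium, chloride, glucose, magnesium and phosphate the same table says "Both highest value and lowest value".

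**Use.** SAP Section 8.5 says "Laboratory data will be summarized by timepoint and for the overall worst post-baseline value", using descriptive statistics and including unscheduled results. The Appendix 3 grades serve other outputs: clinically notable values, shift tables of the baseline grade against the grade at each visit, and a count and listing of subjects whose grade rises by two or more. Section 8.5 does not say which post-baseline value is graded for that last summary.

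**Sampling.** Routine post-baseline hematology is drawn at EOT. At the post-therapy evaluation (PTE), Protocol Section 9.5.1 says "hematology & chemistry will be performed only if clinically significant abnormalities were noted at EOT".

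**The concern.** Two rules for one parameter do not fit together. The grading looks almost entirely upward, while the worst-value rule looks only downward.

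On the low side, a band meant to represent normal reaches down to 1,000/mm3. A substantial fall in WBC can therefore leave no trace in the grade-based outputs until it crosses 1,000, where the grade jumps from 0 to 4.

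On the high side, the worst-value summary discards a raised count whenever a lower one follows. The protocol makes this selective, because scheduled repeat hematology is reserved for women whose EOT result was clinically significantly abnormal. Those with two scheduled post-baseline values are the ones most likely to have an abnormal first value, and the summary would report the recovery instead.

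At stake is the accuracy of the hematology safety tables in a dose-finding study. No efficacy result depends on it.

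**Working it through.** The plan gives no figure to reproduce, so the check applies its rules to test values. The cut-points come from SAP Appendix 3 and the direction of worst from Appendix 2. The individual counts are illustrative assumptions.

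**1. Low counts against the WBC row**

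| Baseline | Post-baseline | Grades | Shift shown |
|---|---|---|---|
| 6,000 | 1,200 | 0 to 0 | none |
| 5,000 | 1,100 | 0 to 0 | none |
| 5,000 | 999 | 0 to 4 | +4 |
| 12,000 | 1,500 | 1 to 0 | -1 (improvement) |

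No value below 11,000 falls in Grades 1 to 3. Counts of 1,100 and 999 differ by 101 cells/mm3 but by four grades. Because fixed-value grades ignore the laboratory's range, a laboratory lower limit does not alter any of these results.

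**2. WBC row against the absolute neutrophil count (ANC) row**

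In Appendix 3 ANC is Grade 0 only above 1,500, and 1,000 to 1,500 is Grade 1. Neutrophils are a subset of white cells, so ANC ≤ WBC. If WBC lies between 1,000 and 1,500, then ANC ≤ 1,500 and its grade is at least 1, while WBC is Grade 0. This conflict appears inside the table, with no outside normal range needed.

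**3. Direction of worst against direction of grading**

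- Hemoglobin, neutrophils and platelets: graded low, worst is lowest.
- Transaminases, GGT, alkaline phosphatase, amylase, lipase, bilirubin, urea, uric acid and creatinine: graded high, worst is highest.
- Sodium, potassium, glucose and calcium: separate high and low rows, worst is both.
- Magnesium and phosphate: graded low only, worst is both.
- WBC: Grades 1 to 3 high only, worst is lowest only.

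Among these parameters, WBC is the only one whose worst value is taken solely from the side without Grades 1 to 3.

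**4. A raised EOT count with a lower repeat**

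Take 16,000 at EOT and 8,000 on repeat.

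- Overall worst under Appendix 2: min(16,000, 8,000) = 8,000. The 16,000 is absent from this summary.
- EOT shift table: 16,000 lies in 15,000 to 30,000, so Grade 3 is shown.
- Increase of two or more grades, from a baseline of 6,000 (Grade 0): using the highest visit grade, 3 - 0 = 3 and the subject is counted. Grading the Appendix 2 worst value instead, 8,000 is Grade 0, 0 - 0 = 0 and she is not counted. Section 8.5 does not choose between the two.

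**The case against.** The strongest reply is that little is actually lost. Section 8.5 applies the worst value only to descriptive statistics, and the shift tables are by visit. A count of 16,000 at EOT, if drawn within the visit window, still appears in the by-visit statistics and as Grade 3 in the EOT shift table, and it is flagged in the listings. Low counts also remain partly visible: the lowest-value summary is built to catch them, listings carry an L flag, ANC has its own Grades 1 to 4, and any WBC below 1,000 is Grade 4. Worsening of the qualifying infection is recorded as clinical failure (Protocol Section 8.15.5), so that signal does not depend on WBC. All of this stands.

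A reader might therefore infer too much in two ways. One inference is that raised counts vanish from the safety report. The documents do not support that, because the loss is certain only in the overall-worst summary and merely possible in the summary of increases of two or more grades. The other is that the SAP calls all leukopenia normal. That is too broad: it holds from 1,000 up to whatever lower limit the laboratory uses, and the documents state no such limit.

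It can also be said that Appendices 2 and 3 are not matched row for row elsewhere. Magnesium and phosphate take both directions but have only low-side grades, and chloride takes both with no grade row. True, but those cases summarize more than is graded. For WBC the summary leaves out the side where most of the grades lie. Finally, the missing low grades may have been inherited from the external table, which is not available here. That would explain the omission, but the Grade 0 band is the SAP's own addition and still fails its stated purpose.

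**Conclusion.** The point holds as a minor inconsistency in safety reporting, worth correcting because the correction is cheap.

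- The WBC row cannot show a downward shift until the count drops below 1,000/mm3, which defeats the stated reason for adding Grade 0 on that side.
- It contradicts the ANC row for total WBC of 1,000 to 1,500.
- The lowest-only rule removes a raised count with a lower repeat from the overall-worst summary. Whether it also affects the summary of increases of two or more grades depends on a choice the SAP leaves open.

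The number of subjects affected cannot be derived from the documents. The conclusion assumes that the WBC row was read correctly from the PDF; its bands are contiguous, which makes a table break unlikely. The primary and secondary efficacy analyses are unaffected.

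**What to change.** SAP Section 3.5 provides for amendments before database lock. Three changes are needed.

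1. **Appendix 2:** change the WBC entry to "Both highest value and lowest value", the SAP's existing convention for two-sided parameters.
2. **Appendix 3:** split WBC into two rows, as for sodium and potassium. The high row keeps the printed limits, with only counts above 30,000 in Grade 4. The low row takes the present limit below 1,000 and adds fixed cut-points for the lower grades. The sponsor should set these and reconcile them with the ANC row, so that a total count which forces an abnormal ANC grade is not itself Grade 0. Fixed cut-points are needed because tying the row to the laboratory's lower limit would break the SAP's rule for fixed-value grades.
3. **Section 8.5:** state that an increase of two or more grades is judged on the highest grade at any post-baseline visit, separately for the high and low rows.

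The cost is small table edits, one added sentence, a sponsor decision on the low-side cut-points and minor programming. No new data are required.

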APPENDIX 4 CONCOMITANT MEDICATION START DATE IMPUTATION

Prior and Concomitant Medication Start Date Imputation

Parameter	Type of Medication	Imputation
Start date for con meds	Non-Antibacterial	If it cannot be determined whether or not the start date of a medication (non-antibacterial) is prior to the first dose of study drug, it will be assumed that the medication was received prior to the first dose of study drug.
	Antibacterial	Missing start dates for antibacterials will be queried for a value. If it cannot be determined whether or not the start date of an antibacterial is prior to the first dose of study drug, it will be assumed that the medication was received prior to the first dose of study drug unless the indication notes that the medication was received after the first dose of study drug.
Stop date for con meds	Non-Antibacterial	If it cannot be determined whether or not the stop date of a medication (nonantibacterial) is after the first dose of study drug, it will be assumed that the medication was received after the first dose of study drug
	Antibacterial	Missing stop dates for antibacterials will be queried for a value. If it cannot be determined whether or not the stop date of an antibacterial is after the first dose of study drug, it will be assumed that the medication was received after the first dose of study drug unless the indication notes that the medication was received prior to the first dose of study drug. If it cannot be determined whether the antibacterial was received prior to the assessment of Early Clinical Response, the EOT and/or the PTE Visit, the antibacterial will be assumed to have been received through the PTE Visit.

Document Approvals

Approved Date:

Approval Task Verdict: Approve	[REDACTED]	23-May-2019 15:34:12 GMT+0000
Approval Task Verdict: Approve	[REDACTED]	23-May-2019 16:00:39 GMT+0000
Approval Task Verdict: Approve	[REDACTED]	31-May-2019 15:29:40 GMT+0000
Approval Task Verdict: Approve	[REDACTED]	03-Jun-2019 13:05:16 GMT+0000
Final Approval Task Verdict: Approve	[REDACTED]	03-Jun-2019 13:06:05 GMT+0000
